4.5 PHARMACOKINETIC AND PHARMACODYNAMIC ANALYSES

Individual and mean plasma concentrations from the oseltamivir population PK model at each sampling time-point for oseltamivir and oseltamivir carboxylate will be presented by listings and descriptive summary statistics, including means, geometric means, medians, ranges, standard deviations and coefficients of variation. Individual and mean concentration-versus-time profiles will be plotted on linear and semi-logarithmic scales.

Plasma concentration data from sparse sampling will be analysed by the clinical pharmacologist using an established population PK model to determine key exposure parameters defined in Section 2.2.4. Note: For IC children (≤ 12 years) and adolescents ($> 12 - \leq 17$ years), plasma oseltamivir and oseltamivir carboxylate concentrations will be modeled in NONMEM using a structure similar to a comprehensive population PK model which was previously developed using oseltamivir and oseltamivir carboxylate plasma concentration data from non-IC children and adults (ages 1 to 80 years).

The PK parameters will be listed and summarized by treatment group using descriptive summary statistics including means, geometric means, medians, ranges, standard deviations and coefficients of variation.

Exposure-response relationships will be presented in the CSR through the use of scatter plots, plotting each of the estimated PK parameters separately against the area under the viral titer curve; the peak viral titer, and the time to cessation of viral shedding. Different symbols will be used to differentiate treatment groups.

All listings and summaries of plasma concentrations and estimable PK parameters will be based on the PKEP population.

Further PK and PK/PD analyses may be carried out by the clinical pharmacology group. This will be reported in a separate report when appropriate.

4.6 SAFETY ANALYSES

No formal hypothesis is being tested to support the co-primary objective of safety. Therefore, there will be no formal statistical comparisons between the two treatment groups. Summaries will be based on the Safety Population and will be provided by treatment and split by age: adults (≥ 18 years) vs. pool of adolescents and children (< 18 years). Only tables for adverse event (AE) and serious adverse event (SAE) [summary and incidence by System Organ Class (SOC) and Preferred Term (PT)] will be provided separately for adolescents (≥ 13 to < 18 years) and children (< 13 years).

All continuous safety outcomes will be given as medians or medians and 95% confidence intervals per treatment arm. All categorical safety outcomes will be shown as frequencies by treatment arm.

4.6.1 Exposure of Study Medication

All treatment data will be listed as collected. The total treatment duration, number of doses, total cumulative doses, missed doses and dose modifications will be summarized by treatment group with the use of descriptive statistics (N, mean, median, SD, and minimum and maximum values).

4.6.2 Adverse Events

Adverse Events (AEs) will be mapped to the Medical Dictionary for Regulatory Activities (MedDRA) preferred terms using the MedDRA version current at the time of reporting, prior to the database lock and will be summarized for the Safety Population according to current sponsor safety standards. Summaries to be presented:

- Overall Incidence of AEs.
- Summary of AEs by relationship to study drug.
- Summary of AEs by body system and Intensity.
- Summary of Serious Adverse Events (SAEs).
- Summary of SAEs by relationship to study drug.

- Summary of SAEs by body system and Intensity.
- Summary of Treatment Emergent AEs resulting in death.
- Summary of AEs leading to study or study drug withdrawal.

As well as summarizing all AEs overall, summaries by treatment phase (on treatment, off treatment) will be presented, where on treatment is defined as an AE starting during treatment or up to 2 days after the last dose, and off treatment is defined as any AE starting more than 2 days after the last dose.

Multiple reports of an event by a subject will only be counted once for tabulations of adverse event incidences, with the most severe intensity being used. All AEs reported on treatment will be considered to be treatment emergent.

4.6.3 Laboratory Data

Blood samples for planned central laboratory tests for safety evaluation of clinical chemistry and haematology are collected at baseline (pre-dose Day 1) and Day 11/End of Treatment. Results will be listed and summarized for the Safety Population, Adults (≥ 18 years) separately from adolescents and children (≤ 17 years). Summaries to be presented:

- Change in baseline to Day 11 will be summarized using descriptive statistics (N, Mean (STD), Median, Min, Max)
- Incidence of marked laboratory abnormalities will be summarized for adults only as per Roche [REDACTED]
- Unscheduled laboratory results will not be included in any of the summaries. If a test was repeated on the same day, the average result will be used in the summary tables. If the scheduled Day 11 laboratory test was taken after the end of treatment, these off treatment results will still be presented in the summaries.

Historical and Day 1 (Protocol versions A and B only) creatinine clearance, CD4 counts and white blood cell (WBC) counts will be listed, where available. CD4 counts will be summarized separately using descriptive summaries for patients only with the inclusion criteria “HIV with a most recent CD4 count $<500/\text{mm}^3$ (or $<25\%$ in children ≤ 5 years old) within the last 6 months and, in the investigator’s opinion, considered immunocompromised”.

4.6.4 Vital Signs

Vital sign measurements including weight, temperature, respiratory rate, blood pressure (position not specified) and pulse rate are planned on Days 1, 2 or 3, 6, 8 and Days 11, 15 and 40. These will be listed and summarized for the Safety Population (adults will be summarized separately from adolescent and children) according to current sponsor safety standards.

4.6.5 Tissue rejection and/or GVHD in transplant patients

The proportion of transplant patients in the safety population who experience tissue rejection and/or GVHD will be summarized by treatment group and age

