Study NV20234 is a double-blind, randomized, stratified multi-center trial of conventional and double dose oseltamivir in immuno-compromised (IC) patients. The conventional dose in adults (≥ 18 years of age) and adolescents (from ≥ 13 to < 18 years of age) is 75 mg twice daily (BID) for 10 days. In children (from 1 to < 13 years of age) the conventional doses are 30, 45, or 60 mg BID for 10 days based on body weight. Immunocompromised (IC) patients who develop an influenza-like illness with confirmed influenza from a positive rapid diagnostic test, PCR, or viral culture will be enrolled during the influenza season. Patients will be stratified by:

- Transplant type: hematopoietic stem cell transplant [HSCT] vs. solid organ transplant [SOT] (Protocol Version A and B) or transplant status yes vs. no (Protocol Version C onwards).
- The time between onset of influenza symptoms and treatment start (up to 48 hours) (≤ 24 hours vs. > 24 hours) (Protocol Version A and B) or the time between onset of influenza symptoms and treatment start (up to 96 hours) (≤ 48 hours vs. > 48 hours) (Protocol Version C onwards).
- Influenza vaccination status for current influenza season (yes vs. no).
- Age (≤ 12 years vs. > 12 years).

See section 4.4.5 for further description of subgroup analyses.

2.1 **PROTOCOL SYNOPSIS**

The Protocol Synopsis is in [Appendix 1](#). For additional details, see the Schedule of Assessments in [Appendix 2](#).

2.2 **OUTCOME MEASURES**

All endpoints (safety, resistance, efficacy and PK) are defined in the SAP (descriptions of the endpoints are in Section 2 and the statistical methods used to describe the endpoints are described in Section 4). There are two co-primary endpoints – safety/tolerability and resistance. It is worth noting that the primary endpoint of this study changed during the course of the study. ‘Time to Resolution of All Influenza Symptoms’ was the primary endpoint in versions A

and B of the protocol. However, this endpoint was relegated to a secondary endpoint to reflect the change in objectives introduced in Protocol Version C.

Baseline is defined for all endpoints as the pre-dose reading on Day 1.

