2.2.5 Safety Outcome Measures

The endpoints used to support the co-primary objective of safety are the following:

- Incidence and severity of AEs (including influenza-associated complications and abnormal findings from physical examinations), SAEs, and reasons for the discontinuation of any study medication. All SAEs and AEs will be tabulated including their clinical severity.
- Change from baseline in vital signs (weight, temperature, respiratory rate, blood pressure and pulse rate).
- Change from baseline in laboratory parameters (AST, ALT, total bilirubin, urea, creatinine, CBC and differential blood cell count, i.e. neutrophils, lymphocytes, monocytes, eosinophils, basophils).
- Lab abnormalities by baseline and visit status (see SOP COG 3007 for expected normal ranges).
- Incidence of tissue rejection or GVHD (Graft Versus Host Disease) in transplant patients.

Note: Incidence of transplant rejection or GVHD in transplant patients has been defined in the protocol as both a primary and secondary endpoint. It will be reported as a primary safety endpoint.

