3. STUDY CONDUCT

3.1 RANDOMIZATION

Patients will be randomized 1:1 to conventional oseltamivir or double dose oseltamivir, stratified according to 4 binary stratification factors. Patients randomized under Protocol versions A and B will be stratified according to transplant (SOT vs. HSCT); time between onset of influenza symptoms and treatment start (≤ 24 hours vs. > 24 hours); influenza vaccination status for current influenza season (yes vs. no), and age (≤ 12 years vs. > 12 years).

Patients randomized under Protocol C onwards will be stratified according to transplant (yes vs. no), time between onset of influenza symptoms and treatment start (up to 96 hours, ≤ 48 hours, > 48 hours), influenza vaccination status for current influenza season (yes vs. no) and by age (≤ 12 years vs. > 12 years). As only transplant patients were enrolled during Protocol A and B, at this time, the randomization was not stratified by transplant status.

The master randomization list is an un-stratified randomization list implemented in the Interactive Voice/Web Recognition System (IxRS) using a dynamic block allocation algorithm to centrally assign patients to the correct strata.

Following the release of TAI, the treatment assignments from the IxRS listing will be checked against the master randomization list to ensure the correct treatments have been assigned. Furthermore, the date and time of randomization will be checked against the date and time of first dose to ensure patients were randomized prior to receiving treatment. Any errors noted will be listed as protocol deviations in the clinical study report (CSR).

Any patients who were assigned to the incorrect strata level at randomization will have the strata information corrected for reporting purposes but the original randomization will remain unaltered.

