6. APPENDIX 1: PROTOCOL SYNOPSIS

TITLE: A DOUBLE BLIND, RANDOMIZED, STRATIFIED, MULTI-CENTER TRIAL EVALUATING CONVENTIONAL AND DOUBLE DOSE OSELTAMIVIR IN THE TREATMENT OF IMMUNOCOMPROMISED PATIENTS WITH INFLUENZA

PROTOCOL NUMBER: NV20234

VERSION NUMBER: F

EUDRACT NUMBER: 2006-002468-24

IND NUMBER: 53,093

TEST PRODUCT: oseltamivir (Tamiflu® RO 64-0796)

PHASE: IIIb

INDICATION: Treatment of influenza in immunocompromised patients

SPONSOR: F. Hoffmann-La Roche Ltd

Objectives

Primary

To evaluate prospectively the safety and tolerability of oseltamivir for the treatment of influenza in IC patients under standard and double dose, and characterize the effects of oseltamivir in IC patients on the development of resistant influenza virus (see 4.6).

Secondary

To evaluate the effects of conventional and double dose oseltamivir in IC patients on:

- The population pharmacokinetics of *both oseltamivir and oseltamivir carboxylate* in IC patients with confirmed influenza infection, through the application of established population pharmacokinetic (PK) models to the sparse plasma concentration data generated.
- The virologic course of influenza (proportion shedding and viral loads at different timepoints)
- The time to resolution of influenza symptoms
- The clinical course of influenza (fever, symptoms, secondary illnesses as evidenced by otitis media, bronchitis, pneumonia, or sinusitis)
- To explore the relationship of metrics of exposure (e.g., AUC, C_{min}) to relevant pharmacodynamic endpoints

Study Design

Description of Study

This is a double-blind, randomized, multi-center trial of twice daily, conventional and double dose oseltamivir for the treatment of influenza in IC patients. Patients will be stratified by age (<13 vs. >12 years), transplant status (yes vs. no), time since onset of flu symptoms and treatment start (up to 96 hours) (≤ 48 vs. >48 hours) and vaccination status (yes vs. no).

Number of Patients

A minimum of 166 (83 per arm) to allow an adequate number of influenza A patients per arm; including 50 transplant recipients *and at least 15 paediatric patients*.

Number of Centers

Approximately 125 centers in the Northern and Southern Hemispheres

Target Population

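### Rejection and/or GVHD, a primary safety endpoint, is planned as one pooled proportion over all transplant patients, so it depends on the transplant mix and can mask a change in either event

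*SAP*

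**What the plan says.** SAP Section 2.2 states: "There are two co-primary endpoints – safety/tolerability and resistance". Section 2.2.5 lists, among the endpoints for the safety objective, "Incidence of tissue rejection or GVHD (Graft Versus Host Disease) in transplant patients", and adds: "It will be reported as a primary safety endpoint".

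The analysis is in Section 4.6.5: "The proportion of transplant patients in the safety population who experience tissue rejection and/or GVHD will be summarized by treatment group and age". No split by event or by transplant type is stated. Under Section 4.6, categorical safety outcomes are shown as frequencies by arm, with no formal comparison between the dose groups. The Statistical Methods part of the synopsis (Appendix 1) says that the safety outcomes, this one included, will be set against the drug's known safety profile.

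On randomisation, Section 3.1 says: "Patients randomized under Protocol versions A and B will be stratified according to transplant (SOT vs. HSCT"), and then: "Patients randomized under Protocol C onwards will be stratified according to transplant (yes vs. no"). Section 2 describes the same change. The only planned transplant subgroup (Section 4.4.5) is status yes or no, and it concerns time to resolution of symptoms. The synopsis plans at least 166 patients, "including 50 transplant recipients".

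**The concern.** The numerator combines two events and the denominator combines two kinds of patient. GVHD arises mainly after HSCT and rejection mainly after SOT. The SAP does not say so itself, but its use of type as a stratification factor in versions A and B treats the groups as distinct.

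Two things follow from pooling:

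- The composite is a weighted average whose weights are the SOT and HSCT shares. If the event rates differ by type, its level changes with the mix. For patients enrolled from version C onwards, that mix is not balanced between arms by design.
- A change in one event is diluted by patients who are hardly at risk of it, or offset by an opposite change in the other event. This happens even when the arms are perfectly balanced on type.

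What is at stake is how the result can be read. Nothing is tested, so the descriptive rate is all the reader has. A blended rate is hard to set against any external figure for rejection or for GVHD.

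**Working it through.** **The plan's own figures.** Section 4.6.5 gives none. The nearest is Table 1 in Section 2.3: exact 95% intervals at n = 75 per arm, with similar precision said to hold for safety at 83 per arm. Clopper-Pearson limits for 0, 1, 2, 4 and 8 events in 75 reproduce all five rows (for example 0/75: 0.0 to 4.8%; 8/75: 4.7 to 19.9%). Those intervals do not describe this endpoint, whose denominator is transplant patients only.

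**Inputs.**
- Transplant recipients: 50 (Appendix 1), randomised 1:1 (Section 3.1), so about 25 per arm.
- HSCT recipients among the 50: not given. Assumed range 10, 15 or 25.
- Difference in event rate between types: not given. Assumed range 5, 10 or 20 points.
- Type allocated wholly by chance. This is an upper bound on imbalance, because patients from versions A and B were stratified by type. How many transplant patients came from each version is not stated.

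**Step 1: chance imbalance in mix.** Let H be the number of HSCT recipients and K the number of them in one arm of 25. The difference in HSCT share is (2K − H)/25. K is hypergeometric, with variance 25 × (H/50) × (1 − H/50) × 25/49.

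| H of 50 | Variance of K | SD of share difference | Chance of a gap of 20 points or more |
|---|---|---|---|
| 10 | 2.04 | 2 × 1.429/25 = 11.4 points | 7% |
| 15 | 2.68 | 2 × 1.637/25 = 13.1 points | 22% |
| 25 | 3.19 | 2 × 1.786/25 = 14.3 points | 26% |

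**Step 2: effect on the composite.** Shift = share difference × difference in event rate between types. For a 20-point imbalance:
- 0.20 × 5 points = 1 point
- 0.20 × 10 points = 2 points
- 0.20 × 20 points = 4 points

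**Step 3: masking with balanced arms.** Take 25 transplant patients in an arm, SOT rejection at 5%, and GVHD as the only HSCT event (all assumed).
- 5 HSCT, 20 SOT, GVHD 10%: (5 × 0.10 + 20 × 0.05)/25 = 6%.
- 5 HSCT, 20 SOT, GVHD 30%: (5 × 0.30 + 20 × 0.05)/25 = 10%.
- 12 HSCT, 13 SOT: the same rise shows as 7.4% to 17.0%.

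The 20-point rise in GVHD is multiplied by the HSCT share: 20 × 5/25 = 4 points in the first case, 20 × 12/25 = 9.6 in the second.

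**Step 4: precision before and after a split.** Exact 95% limits: 0/25 gives 0 to 13.7% and 2/25 gives 1.0 to 26.0%. After a split by type, the upper limit with no events is 21.8% for 15 patients, 30.8% for 10 and 52.2% for 5.

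**The case against.** The case for leaving the text alone has real force:

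- **No inference is affected.** Section 4.6 disclaims hypotheses and formal comparisons for safety, and this is one of five listed safety measures. This stands.
- **Chance imbalance in mix is ordinary sampling variation.** Take half HSCT, 30% GVHD and 5% rejection as an illustration. The composite is 17.5%, and the SD of the arm difference is sqrt(2 × 0.175 × 0.825/25) = 10.7 points. Mix accounts for 0.25 × 0.25² / (0.175 × 0.825) = 0.0156/0.1444, about 11% of that variance. The rest remains after a split. This stands too.
- **Much can be seen elsewhere.** The adverse event tables by System Organ Class and Preferred Term (Section 4.6) would show the two events separately if they are reported as adverse events. Transplant history is tabulated by arm (Section 4.3), and the data are listed in the study report (Section 4). This stands in part. Those tables use the whole Safety Population, non-transplant patients included, and none gives either event over a type-specific denominator.
- **Risk is predominant, not exclusive.** Graft failure can follow HSCT, so counting rejection only in SOT and GVHD only in HSCT would lose events. This stands, and the fix allows for it.
- **The sentence in Section 4.6.5 ends without a full stop**, so it may be incomplete. That cannot be settled from the text.

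A reader might infer that the dose comparison on a co-primary endpoint is biased, or that most of the denominator is not at risk of each component. The SAP supports neither. Randomisation leaves the mix to chance without favouring an arm, and patients from versions A and B were stratified by type. Nor can most of the same denominator be free of risk for both events when the two groups make it up between them.

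**Conclusion.** The point holds as a weakness of presentation in a primary safety endpoint. The pooled proportion cannot be read as a rejection rate or as a GVHD rate, and no other planned table supplies either one over the patients at risk.

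Masking is the stronger reason to change the table, because it needs no imbalance. The mix effect is smaller: 1 to 4 points at a 20-point imbalance, and a gap that large is far from certain even when type is left entirely to chance. All these sizes rest on assumed type shares and event rates, and on the planned 50 transplant recipients. The total of 166 is a minimum, and larger transplant numbers would reduce the chance imbalance. The premise that the two types face mainly different events comes from outside the SAP.

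The pooled summary is not an error or a contradiction, and it alters no error rate.

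**What to change.** In Section 4.6.5, replace the single proportion by separate summaries of rejection and of GVHD, each within transplant type (SOT, HSCT) by treatment arm. Give the count, the type-specific denominator and an exact 95% CI. Include a row for rejection or graft failure in HSCT recipients, so that no event drops out. Keep the composite as a supplementary line, and show the number of SOT and HSCT recipients per arm beside it.

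The cost is a few table rows. The schedule of assessments (Appendix 2) already names rejection and GVHD, and transplant history is collected at baseline. The drawback is precision: denominators shrink and intervals widen, as step 4 of the working shows. A further split by age would thin the cells more, so age may be better served by counts or a listing. The intervals will not separate the doses, but they will show how little the data say about each event.

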4.7 RESISTANCE

To support the co-primary objective of this study, the proportion and Clopper-Pearson 95% CIs of patients with post-baseline genotypic or phenotypic resistance among all patients will be summarized by treatment group. The mITTi population will be used whenever possible.

In addition, the following outputs will be included:

- Incidence of overall post-baseline resistance (i.e. developed after first visit) by age (≥ 18 years vs < 18 years old) and treatment group, split by flu type and subtype.
- Incidence of overall baseline resistance (i.e. observed at first visit) by age and treatment group, split by flu type and subtype in ITT population. N.B. Patients with baseline resistance are excluded from both ITTi and mITTi populations.
- Profiles (listings) of viral load in \log_{10} vp/mL for patients with phenotypic or genotypic resistance at baseline. Also listings of genotypic resistance and phenotypic outlier samples.
- Incidence of known OC resistance mutations in phenotypic outlier samples compared with phenotypically OC sensitive samples.
- Incidence (in %) of post-baseline resistance in patients with detectable viral shedding (in \log_{10} vp/mL) at EOT and during follow-up period, by treatment group, age (≥ 18 years vs < 18 years old) and flu type and subtype.
- Summary (median and CI) of the TTR by treatment group, split by post-baseline resistance status.
- Summary (median and CI) of the TTR by treatment group in patients with post-baseline resistance, split by flu type.
- Summary of viral load in \log_{10} vp/mL for patients with phenotypic or genotypic resistance at baseline.

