2.2.6.1 Genotypic resistance

Baseline and post-baseline genotypic resistance is defined as the presence of oseltamivir resistance mutations in the NA or HA genes identified by sequencing of influenza viruses isolated from nasopharyngeal samples.

Genotypic resistance calculation: Presence of genotypic resistance (yes/no), together with the specific resistance mutations will be identified (see USPI list in [Appendix 6](#)) for each nasopharyngeal sample and will be listed.

Note: a H274Y-specific RT-PCR assay was performed for some H1N1 samples of season 2008-2009 to determine baseline genotypic resistance and results will be also included.

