2.2.6.2 Phenotypic Resistance

Baseline and post-baseline phenotypic resistance is defined as the presence of phenotypic resistance identified by oseltamivir IC₅₀ determination, using statistical outlier rules and in accordance with the algorithm described in surveillance studies ([Sheu TG et al 2008](#), [Okomo-Adhiambo M et al, 2010](#)).

Phenotypic resistance calculation: The mean IC₅₀ of the baseline (pre dose Day 1 result) samples of all patients will be calculated separately for each virus subtype. Extreme outliers will be defined as any baseline or post-baseline IC₅₀ values > 10-fold the baseline mean IC₅₀. The baseline IC₅₀ distribution statistics (i.e. mean, standard deviation [SD], median, 75th percentile [X_{0.75}]) will then be re-calculated excluding any baseline extreme outliers previously identified. Outliers will be defined as any baseline or post-baseline IC₅₀ values less than 10-fold the baseline mean, but more than three interquartile ranges (IQRs) greater than the

baseline third quartile ($X_{0.75}$) ($> [X_{0.75} + \{3 \times IQR\}]$). Outliers and extreme outliers will be considered to have phenotypic resistance.

Note: the phenotypic resistance algorithm assumes that the IC_{50} samples are normally distributed. Appropriate transformations will be considered if this assumption is not met. Furthermore, alternative algorithms (e.g., fold-changes, pooling of NA subtypes) may be used if the number of IC_{50} samples per NA subtype is considered small.

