4.1.3 Modified Intent To Treat infected (mITT_i) Population

All patients randomized to a particular treatment, regardless of whether they received that treatment or not, and received at least one dose of study drug and with central laboratory confirmation of influenza infection, excluding patients infected with oseltamivir-resistant influenza at baseline, will be included in the mITT_i population. This population will also be used to summarize all efficacy and resistance endpoints because it will render least biased effect estimates. This population was not defined in the protocol.

The definition of oseltamivir-resistant influenza at baseline is defined in Section 2.2.6. Decisions on patient exclusion from the ITT, ITT_i and mITT_i population sets will be made by the statistician and study scientist after database closure. Excluded patients will be documented along with the reason for exclusion.

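### A resistant post-baseline swab is counted as resistance that developed on study even when the patient has no baseline typing result, or only a partial one, which can push the co-primary rate upward

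*SAP*

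**What the plan says.** The synopsis in Appendix 1 of the SAP gives the resistance objective as to "characterize the effects of oseltamivir in IC patients on the development of resistant influenza virus". Section 4.7 turns this into a proportion per arm of "patients with post-baseline genotypic or phenotypic resistance among all patients will be summarized by treatment group". The first supporting output in that section is headed "Incidence of overall post-baseline resistance (i.e. developed after first visit) by age", so the SAP reads a post-baseline finding as resistance that arose during the study.

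The derivations work sample by sample. Section 2.2.6.1: "Baseline and post-baseline genotypic resistance is defined as the presence of oseltamivir resistance mutations in the NA or HA genes identified by sequencing". Section 2.2.6.2 compares each IC50 with the pooled baseline distribution of the virus subtype and concludes: "Outliers and extreme outliers will be considered to have phenotypic resistance". Neither section compares a later sample with the same patient's baseline sample.

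The link to baseline comes from the analysis population. Section 4.7 states "The mITTi population will be used whenever possible", and section 4.1.3 defines mITTi as "excluding patients infected with oseltamivir-resistant influenza at baseline". Entry to mITTi also needs central laboratory confirmation of influenza, but no baseline sequence or IC50.

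**The concern.** Not finding resistance at baseline is different from finding a susceptible virus at baseline. The mITTi exclusion acts only on the first. Take two patients who enter with the same resistant virus. One has a baseline sequence, is recognised as resistant and is excluded. The other has a baseline swab that confirms influenza but gives no sequence and no IC50. That patient stays in mITTi and, if a later swab is resistant, enters the numerator as a case of developed resistance. The classification then depends on whether the baseline assay gave a result, not on what happened under treatment.

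A partial baseline result has the same effect. Section 2.2.6.1 notes that "a H274Y-specific RT-PCR assay was performed for some H1N1 samples of season 2008-2009" to establish baseline genotypic resistance. If that was a patient's only baseline test, it cannot rule out the other N1 substitutions listed in Appendix 6.

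At stake is a co-primary estimate based on few events. The endpoint is an absolute rate in each arm, so randomization between two active doses does not remove the error.

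**Working it through.** **1. The SAP's own figures.** Inputs from section 2.3: 83 enrolled per arm and 90% with confirmed influenza. 83 × 0.90 = 74.7, rounded to 75. The exact Clopper-Pearson limits for x events in n are the 2.5% quantile of Beta(x, n − x + 1) and the 97.5% quantile of Beta(x + 1, n − x). At n = 75:

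| Events | Rate | 95% interval | Table 1 |
|---|---|---|---|
| 0 | 0.0% | 0.0–4.8 | 0.0–4.8 |
| 1 | 1.3% | 0.0–7.2 | 0.0–7.2 |
| 2 | 2.7% | 0.3–9.3 | 0.3–9.3 |
| 4 | 5.3% | 1.5–13.1 | 1.5–13.1 |
| 8 | 10.7% | 4.7–19.9 | 4.7–19.9 |

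Table 1 is correct. The point concerns what is counted, not the interval method.

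**2. Effect of one misclassified patient.** 1/75 = 1.3 percentage points.
- 0/75 becomes 1/75: the upper limit rises from 4.8% to 7.2%.
- 1/75 becomes 2/75: the rate doubles from 1.3% to 2.7%.
- 2/75 becomes 3/75: 2.7% (0.3–9.3) becomes 4.0% (0.8–11.2).

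**3. What the rules do with each baseline result, given a resistant later swab.**
- Baseline typed and resistant: excluded from mITTi, not counted.
- Baseline typed and susceptible: counted, and rightly called developed.
- Baseline not typed: stays in mITTi and is counted as developed; origin unknown.
- Baseline tested for one mutation only, with a different mutation later: stays in mITTi and is counted as developed; origin unknown.

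**4. Is there a rule elsewhere?** Section 4.9 deals with missing symptom scores and temperatures only. Footnote c to the schedule in Appendix 2 plans mutation testing of baseline swabs but does not say what happens when it fails. Section 2.2.6 assigns flu type for mixed infections at the first time point that has RT-PCR results, which allows for a missing baseline result. Section 2.2.2.3 drops patients without a suitable assay from the shedding analysis; resistance has no such rule.

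**5. Possible size, on assumed inputs.** Let u be the share of mITTi patients without baseline typing, and r the share of those whose virus was already resistant and is seen as such later. The SAP gives neither. Expected false cases per arm = 75 × u × r.
- u = 5%, r = 1%: 0.04 cases, 0.05 points.
- u = 10%, r = 5%: 0.38 cases, 0.5 points.
- u = 20%, r = 5%: 0.75 cases, 1.0 point; chance of at least one = 1 − (1 − 0.01)^75 = 53%.
- u = 20%, r = 20%: 3.0 cases, 4.0 points.

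The last line needs both assumed upper values together.

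**6. What reporting both ways would show.** Suppose 4 of 75 are resistant after baseline and one of them has no susceptible baseline result. Counted as emergent: 4/75 = 5.3% (1.5–13.1). Counted as not emergent: 3/75 = 4.0% (0.8–11.2). If two of the four are of unknown origin, the second figure is 2/75 = 2.7% (0.3–9.3).

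**The case against.** The strongest reply is that section 4.7 already states the intended concept. It sets resistance arising after the first visit against resistance observed at the first visit, and sections 2.2.6.1 and 2.2.6.2 may be meant only to define a resistant sample. That is a fair reading of the intention. It still leaves a programmer without a rule for a patient with no baseline result, and the literal derivation counts that patient.

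Three stronger readings might be inferred, and the SAP does not support them.
- That every resistant post-baseline sample counts. In mITTi it does not, because patients with detected baseline resistance are excluded, and a note in section 4.7 repeats this.
- That baseline typing is shown to have been uneven. The note on the H274Y assay says its results are also included; it does not say that those samples lacked sequencing, and baseline mutation testing was planned.
- That Table 1 gives expected event counts. It gives the precision that would follow from certain observed rates.

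It can also be said that resistance results are listed by sample, so a reader could find cases without a baseline result, and that for a safety-type endpoint it is cautious to count uncertain cases. Both points have force. Neither makes the headline proportion a measure of development, and giving the interval both ways keeps the cautious figure.

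Finally, requiring the baseline result to come from the same method as the later finding would go too far. A patient with a susceptible baseline sequence and a later IC50 outlier would move to unknown origin, and real emergence could be under-counted.

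**Conclusion.** The point holds for patients in mITTi with no baseline typing result, or only a partial one. Followed literally, the SAP counts a resistant later swab from such a patient as developed resistance, and this can push the co-primary rate upward by 1.3 points per patient at 75 per arm.

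The total size cannot be derived from the SAP. The range of 0.04 to 3.0 false cases per arm rests wholly on the assumed shares. A reader might conclude that the reported rate will be too high overall; that does not follow. The rate is taken among all patients, so those with no typable post-baseline sample stay in the denominator and pull it down. The net direction is therefore undetermined.

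A secondary weakness is that mITTi is to be used only where possible and no fallback is named. If the fallback were ITT as defined in section 4.1.1, patients with known baseline resistance would not be removed by the population definition either.

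**What to change.** In section 4.7:
- Count resistance as treatment-emergent when the patient has a susceptible baseline result: a sequence covering the position concerned, or an IC50. Either method suffices.
- Show patients with post-baseline resistance and no such baseline result by arm, in a separate row for unknown origin.
- State, by arm, the number of patients with paired baseline and post-baseline results.
- Give the Clopper-Pearson interval twice, with the unknown-origin patients counted as emergent and as not emergent. Use the same stated denominator for both, so that they differ only in this classification.

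The cost is one definition, one table row, a count of paired results and a second interval; no new data are needed. The downside is that a few patients may move to the unknown-origin row and the main rate may be slightly lower. If every baseline was fully typed, the row is empty and the two intervals agree.
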